### Our hypothesis is that:

1. 3D parameters could bring additional information in pre-operative, surgery and post-op control.

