## STUDY DESIGN

---

The study will be prospective, randomized, occurring in New-York Presbyterian Hospital. The study design includes 4 arms:

- Cohort A: Adults and standard of care (EOS biplane acquisition). Planning performed with current practice.
- Cohort B: Adults and standard of care (EOS biplane acquisition). Planning performed with additional 3D information provided by 3D modeling on sterEOS software (FDA approved)
- Cohort C: Children and standard of care (EOS biplane acquisition). Planning performed with current practice.
- Cohort D: Children and standard of care (EOS biplane acquisition). Planning performed with additional 3D information provided by 3D modeling on sterEOS software (FDA approved)

For cohort B and D, 3D additional information will be provided to the surgeons. This information may help them to better understand the pathology and plan the procedure.

Radiographic, clinical parameters and freeform observations by the surgeon will be collected at pre-operative, peri-operative and post-operative steps, for patients who meet the inclusion criteria and signed the informed consent. The recorded parameters and freeform observations will be compared between patients of cohort A and B, and cohort C and D.

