#### **EOS exclusion Criteria:**

- Patients with supernumerary vertebrae (one extra or one less thoracic or lumbar vertebrae)
- Patients with hemivertebrae
- Insufficient quality of images to perform the 3D modeling with sterEOS software

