#### **EOS exclusion Criteria:**

- Patients younger than 7 years old
- Patients with supernumerary vertebrae (one extra or one less thoracic or lumbar vertebrae)
- Patients with hemivertebrae
- Insufficient quality of images to perform the 3D modeling with sterEOS software

**Note:** Every patient who only meets the EOS exclusion criteria will be automatically transferred in the A cohort if they are over 18, and in the C cohort if they are younger than 18 years old.

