## **Data Analysis and Data Monitoring**

This pilot study is mainly an observational study. The aim of the study is only to observe the value of additional information provided by 3D modeling with sterEOS software.

At the end of the 6 first months of the study, a first data analysis will be performed at Columbia with the available data in order to have some preliminary results. The final data analysis will be performed at the end of the data collection, when every patients enrolled will have the full assessment (preop, periop and post-op data). This analysis will be performed at EOS Imaging with the shared data provided by Columbia.

Descriptive analysis (mean, range and standard deviations) will be calculated for all the parameters and HRQOL data with Excel software. Correlations will be performed using Pearson correlation coefficient, and Student's t-Test will be utilized to determine if these correlations are significant, with significant p-value set at 0.05.

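### The promised A-versus-B and C-versus-D comparisons have no stated estimate or analysis set, and the one-way transfer of EOS-unsuitable patients into A or C can confound the cohorts as labelled

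*Combined protocol and SAP*

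**What the plan says.** Study Design, on the design: "The study will be prospective, randomized". On its use: "The recorded parameters and freeform observations will be compared between patients of cohort A and B, and cohort C and D". A and C are planned by current practice; B and D have added 3D information.

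Data Analysis and Data Monitoring is the only analysis section. It offers summaries, "Descriptive analysis (mean, range and standard deviations) will be calculated for all the parameters and HRQOL data with Excel software", and Pearson correlations, with "t-Test will be utilized to determine if these correlations are significant, with significant p-value set at 0.05". It does not say that the summaries are by cohort, which variables are correlated, or who belongs to a cohort for analysis.

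The Note closing the children's EOS exclusion criteria says: "Every patient who only meets the EOS exclusion criteria will be automatically transferred in the A cohort if they are over 18". Those under 18 go to C in the same way. The criteria in both age groups are supernumerary vertebrae, hemivertebrae and "Insufficient quality of images to perform the 3D modeling with sterEOS software". Children have one more: "Patients younger than 7 years old". The Note does not say whether transfer comes before or after allocation.

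**The concern.** Randomisation earns its place here only if A and B, and C and D, differ by nothing systematic except the 3D information. The transfer rule runs in one direction: unsuitable patients can be in A or C, but the rule removes them from B and D. A difference between labelled cohorts therefore mixes any effect of 3D planning with the effect of unusual anatomy, poor images or very young age.

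The analysis section offers no protection. It names neither the contrast nor the patients in it, so both could be settled after the data are seen. A correlation between two parameters, with no stated use of the cohort label, does not deliver the comparison that Study Design promises.

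**Working it through.** **The text.** Study Design commits to two between-cohort comparisons. The analysis section contains a summary of all parameters and a test of correlations. Its nearest approach to an analysis set is the remark that the final analysis waits until everyone has a full assessment, which is about timing. Patient Enrollment makes complete data a condition of enrolment. Neither says whether patients are grouped as allocated or as labelled.

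**No plan figure to reproduce.** Number of Subjects anticipates about 160 patients, with no split by cohort, allocation ratio, effect size or SD. What follows is an illustration.

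**Assumed inputs (not in the documents).** 80 patients per age group; 1:1 allocation; EOS-excluded share f = 5%, 10% or 20%; excluded patients differ in mean outcome by 0.5 SD; no true effect of 3D planning.

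**Composition, with transfer before allocation.**
- Excluded patients: 80f
- Suitable patients per cohort: 40(1 − f)
- A (or C) as labelled: 40(1 − f) + 80f = 40(1 + f)
- Excluded share of A (or C): 80f / [40(1 + f)]; share of B (or D): 0
- Spurious shift: share × 0.5 SD

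| f | Excluded | A v B as labelled | Excluded share of A | Shift |
|---|---|---|---|---|
| 5% | 4 | 42 v 38 | 4/42 = 9.5% | 0.048 SD |
| 10% | 8 | 44 v 36 | 8/44 = 18% | 0.091 SD |
| 20% | 16 | 48 v 32 | 16/48 = 33% | 0.167 SD |

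With a 0.25 SD outcome difference the shifts are 0.024, 0.045 and 0.083 SD. With no difference they are zero.

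**Transfer after allocation.** A begins with 40 patients, of whom 40f are unsuitable, and gains 40f from B. It again has 40 + 40f patients, 80f of them unsuitable, so the share and shift are unchanged.

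**Dropping only the transferred patients.** If transfer follows allocation, this leaves A with 40 patients, 40f of them unsuitable, and a shift of f × 0.5 = 0.025, 0.05 or 0.10 SD. That is an upper bound under these assumptions, because it supposes that no unsuitable patient allocated to A or C is recognised. The Data Collection tables schedule no 3D modelling in A or C, so unusable images may go unnoticed there. But age needs no image, and the anatomical criteria could be looked for on the pre-operative films scheduled in every cohort.

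**Precision cost of restricting to suitable, randomised patients.** The 95% half-width in SD units is t(0.975, df) × √(1/n₁ + 1/n₂), with df = n₁ + n₂ − 2 and a common SD. Adjusting for the pre-operative value multiplies by √(1 − ρ²) and costs one df. The adjusted columns use an assumed ρ = 0.5.

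| f | Pooled, unadjusted | Restricted, unadjusted | Widening | Pooled, adjusted | Restricted, adjusted |
|---|---|---|---|---|---|
| 5% | 0.4457 (42 v 38) | 0.4571 (38 v 38) | 2.6% | 0.386 | 0.396 |
| 10% | 0.4474 (44 v 36) | 0.4701 (36 v 36) | 5.1% | 0.388 | 0.407 |
| 20% | 0.4543 (48 v 32) | 0.4997 (32 v 32) | 10% | 0.394 | 0.433 |

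The widening is about the same adjusted or not. Adjustment narrows both analyses and does not pay for the restriction.

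**The case against.** The strongest reply is that this is a pilot, described in its own analysis section as largely observational, whose aim is only to observe what 3D modelling adds. The hypothesis is modest: "3D parameters could bring additional information in pre-operative, surgery and post-op control". Radiographic Data has the 2D parameters measured in 3D as well, so correlations can bear on that hypothesis, and the summaries could simply be tabulated by cohort. Much of this stands. No formal between-cohort test is needed, and the correlations have a descriptive role. But Study Design still promises the comparisons, and even a descriptive table by cohort needs a rule for who is in each column.

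It is also fair that the bias may be small. Transferred patients might be few or might not differ on the outcome. The hemivertebrae route may add few, because congenital scoliosis is already excluded in both age groups.

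Two stronger readings are not supported. A reader might infer that the plan rules out a between-cohort analysis; it is silent, which is different. A reader might also infer that the rule is shown to have defeated randomisation. The documents establish a difference in make-up, but give neither the number transferred nor their outcomes, so the presence and size of bias on a given variable cannot be established from them.

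**Conclusion.** The point holds and should be fixed. The missing contrast and analysis set, and the one-way transfer, are plain on the text. Followed as written, the plan would compare cohorts of different composition, and the comparison is confounded wherever transferred patients differ on the variable compared. In children a difference in make-up is built in as soon as any child under 7 is enrolled.

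The size is only illustrative: 0.05, 0.09 or 0.17 SD at EOS-excluded shares of 5%, 10% or 20%. It rests wholly on the assumed group size, allocation ratio, shares and 0.5 SD difference. Its direction is unknown. Confidence is high on the gap in the plan, not on the magnitude of any bias.

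**What to change.** 1. **Note under the EOS exclusion criteria.** Apply the EOS-suitability criteria to every patient before allocation. Patients who fail are not randomised and are reported separately, outside the A-versus-B and C-versus-D comparisons. A patient found unsuitable after allocation is analysed in the allocated cohort. If prior screening is impracticable, either analyse all randomised patients as allocated, or apply the same pre-operative criteria to both cohorts, blind to outcome, and exclude failures from both sides.

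2. **Data Analysis and Data Monitoring.** State that B minus A and D minus C differences with 95% confidence intervals will be estimated in that set for the 3–4 month HRQL and 2D radiographic parameters. Adjust for the pre-operative value, which the Data Collection tables already schedule in every cohort. Label these contrasts exploratory and keep the correlations as descriptive.

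**Cost.** Two changes of wording, a few regression models on data already scheduled, and a record of each patient's suitability and allocation. No visit or imaging is added. Under the illustration, A or C shrinks (48 to 32 at a 20% excluded share) while B or D stays the same, and intervals widen by about 2.6%, 5.1% or 10% against a like-for-like pooled analysis. If image quality can be judged only by attempting the 3D model, some extra attempts are needed for patients later allocated to A or C. Late-found unsuitable patients kept in B or D dilute the contrast in proportion to their share.

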## **Data storage**

The research team will follow rigorous procedures to protect confidentiality of study participants. Access to identifying information will be limited to those whose project roles demand it, and only for the period of time in which they need it. All electronic data will be stored on encrypted endpoint devices and a certified multi-user system.

Once the relevant research data is collected, the direct identifiers will be removed from the research data to maintain protection of PHI, the subject's data will be linked to a Study ID Number, and the link to direct identifiers will be stored in a separate master list only accessible by study personnel listed on this protocol. At completion of the study, the link to direct identifiers will be destroyed.

At no time and under no circumstances will any directly identifiable patient information or data be shared with any outside institutions not otherwise specified, individuals, or other entities. All funding agencies, the Columbia University Institutional Review Board, and the US Department of Health and Human Services will have the right to inspect medical records related to this study for the purpose of verifying data and patient confidentiality practices.

## **Data release:**

At the end of the data collection period, coded research data (global spreadsheets) will be shared with EOS Imaging France, where the link to identifiable information will remain at Columbia.

To perform the transfer from Columbia to EOS Imaging, the data will be sent via encrypted email. Patient will agree to this release as stipulated in the consent form.

## **Risk**

No further risks for physical injury are associated with participation in this study. This study will only observe the value of additional information and will not change the current practice for all the patients enrolled.

#### **Costs to the Subject**

Any imaging and surgical component used in the present study will be considered part of the standard of care. The patient may want to discuss this with his/her insurance carrier in advance. The patient will be responsible for any co-payments and/or deductibles for services rendered.

